4.1 Study Participants

Subjects will be parents/caregivers and their children in grades K-4 in one of three Counties: Cuyahoga County (East Cleveland City School District (ECCSD, Cleveland, OH) and Bedford City School District (BCSD, Bedford, OH)); Cowlitz County (CC, WA); and Lewis County (LC, WA); (See Table 4.1.1 below). The study will be offered to all caregivers and their children including those children with special health care needs. Parent/caregivers and children will be enrolled in the study upon signing the consent/assent form and completing the recruitment and contact form. All enrolled children will receive a dental screening at the beginning of the school year. Following the screening, only parent/caregivers whose child has a tooth with an International Caries Detection and Assessment System (ICDAS) active lesion score of 2 or greater will be randomized and continue further participation in the trial. Caregivers with multiple children in K-4 will receive the same intervention assignment.

Table 4.1.1 School District Information

County	School District	Elementary Schools	K-4 Enrollment
Cuyahoga Co.	East Cleveland City SD	Caledonia, Chambers, Mayfair, Superior	889
	Bedford City SD	Central, Glendale, Columbus, Carywood	1274
Cowlitz Co.	Kelso SD.	Catlin, Wallace	1122
	Longview SD.	Kessler, St. Helens	
Lewis Co.	Central SD.	Jefferson Lincoln	586
	Winlock SD.	Winlock Miller	

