Arm 5 (N=204): The fifth arm (control) is the modified standard letter (based on November 2007 guidelines for Oral Health Screening in Ohio Schools). This letter is consistent with others used across the country and will be used in both the Ohio and Washington sites.

All letters will be sent home with the child on the day of the screening and mailed to the caregiver’s address within 24 hours. The address will be obtained during recruitment and verified with the school secretary.

A description of the recruitment, enrollment, randomization, and follow-up is below:

Caregivers will be recruited at the beginning of the school year and complete baseline forms (consent form, Illness Perception Questionnaire-Revised for Dental (IPQ-RD) questionnaire, and caregiver questionnaire) prior to dental screening and randomization (Figure 4.2.2). Children in K-4 whose parents have consented/assented will receive a screening exam in early October 2015. Caregivers whose children have no cavities or who have emergent needs will not participate further in the clinical trial. The baseline data from discontinued child and caregiver participants will be used only for baseline descriptive comparisons.

At the same time following screening exams eligible caregivers of children with restorative referrals will be randomized. Caregivers will be followed at 2 time points: 2 weeks after the receipt of the intervention letter and 2 weeks prior to the final (exit) study visit examinations in May 2016 (approximately 7 months after the initial dental exam). At both time points caregivers will complete the IPQ-RD and the caregiver questionnaire. A small sub-sample of 60 caregivers will be randomly

sampled from arms 1, 2 and 5 (20 per arm), to complete the IPQ-RD 1 month after enrollment for reliability purposes. All questionnaires will be mailed to the home address and asked to be returned to the class-room teacher or the outreach staff. Further, outreach staff will ensure that the caregivers received and returned the materials through follow-up calls. The schedule and scripts for the call are contained in the MOP (Table 6.1 and Appendix 6). Children will have a follow-up dental exam in May 2016.

[figure not shown]

Figure 4.2.2 Flowchart for Recruitment, Enrollment, and Randomization

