8 STUDY PROCEDURES/EVALUATIONS

The following are the various study procedures and evaluations that will be done during the study:

Administration of questionnaires (IPQ-RD and caregiver questionnaires including demographic information) for caregiver and child information (See Section 3.2, Table 3.2.1; see Appendix C): Caregivers will be asked to complete questionnaires at three time points (baseline prior to screening, 2 weeks after the dental screening examination, and at the end of the school year).

Dental examinations for baseline caries status and primary study outcome: Exams will be performed on the children whose caregivers have consented to their participation. The dental examinations will be done according to the standard caries detection and assessment system termed ICDAS (International Caries Detection and Assessment System). The initial examination (approximately 2 months after the beginning of the school year) will determine a child's need for restorative care which is an inclusion/exclusion criterion for study continuation and randomization. The final examination (approximately 1 month prior to the end of the school year) will be used for the primary study outcome for children enrolled in the RCT.

Administration of the intervention (referral letters) (See Section 6 – Study Intervention): The letter will be sent home with the child and mailed to the caregiver. Confirmation that the letter was received will be obtained through telephone contacts.

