12.2 Sample Size Considerations

The primary aims are to compare dental care receipt among the five intervention groups, overall and separately for each study site (Ohio and Washington).

The five intervention groups are:

Arm 1: CSM referral letter alone (N=204)

Arm 2: CSM referral letter + DIG (N=204)

Arm 3: Reduced CSM referral letter alone (N=24)

Arm 4: Reduced CSM referral letter + DIG (N=24)

Arm 5: Modified Standard letter (N=204)

The utilization will be defined as evidence of dental care through restorations or extractions at the final study visit exam that was previously not found during the baseline exam. All changes will be recorded on a tooth level using ICDAS criteria and then dichotomized at the caregiver level as having obtained or not obtained dental care for their child/children.

There are three treatment comparisons to assess the overall CSM referral letter and DIG: CSM referral letter alone versus standard letter (Arm 1 vs Arm 5), CSM referral letter plus DIG versus standard letter (Arm 2 vs Arm 5), and CSM referral letter alone versus CSM referral letter plus DIG (Arm 1 vs Arm 2). As described below we address the issue of multiple testing, both multiple comparisons and multiple sites, using a gatekeeper approach. By specifying a sequence of tests, this approach will allow for the use of a nominal 0.05 alpha level for each test while maintaining a 0.05 family-wise alpha level for the six tests (three at each study site).

An additional comparison will be conducted to assess the effect of the targeted component (e.g., the ‘timeline’ text): CSM referral letter with and without DIG versus reduced CSM referral letter with and without DIG (Arm 1, 2 vs Arm 3, 4).

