Given the parameter estimates from the above models, we use a model-based standardization approach (Albert et al. 2011) to estimate relative risks (i.e., the ratio of the probabilities of dental usage for a given pair of interventions). A bootstrap approach will be used to obtain a 95% confidence interval for each relative risk. Significance will be determined using a gatekeeper approach to hypothesis testing. Specifically, we will first test for a difference in dental care receipt rates for S vs CSM+DIG (at the 0.05 nominal alpha level). If (and only if) this test is significant, we will proceed to test S vs. CSM alone and CSM vs CSM+DIG (both at the 0.05 nominal alpha level). We will use a similar approach for testing for each site. We will start by testing (for a given treatment comparison) an overall effect (stratifying over sites) at the 0.05 nominal alpha level. If (and only if) this is significant, we will then test (for the same treatment comparison) the effect within each site (at the 0.05 nominal alpha level). A 0.05 family-wise error level is attained in this approach assuming that a (true) effect for S vs. CSM+DIG implies a (true) effect for either S vs. CSM or CSM vs. CSM+DIG (or both), and that an overall effect implies an effect in one or both sites (which is logically the case).

To test the effect of the targeted component (timeline), we will fit the same multivariate generalized linear (specifically, logistic regression) models mentioned above with additional indicator representing reduced text.

Adjustment for Baseline Characteristics: Estimated intervention effects (described above) will be adjusted for the following baseline socio-demographic variables: child's age, race, and caregiver SES, education, and marital status.

Model Assumptions: We will assume that the probabilities of dental care receipt follow the selected logistic regression model (controlling for covariates) mentioned above. We assume that the outcomes for different caregivers (or different schools if a correlation structure for two cluster levels is used) are independent.

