13 SOURCE DOCUMENTS AND ACCESS TO SOURCE DATA/DOCUMENTS

Each participating site will maintain appropriate research records for this study, in compliance with ICH E6, Section 4.9 and regulatory and institutional requirements for the protection of confidentiality of subjects. Each site will permit authorized representatives of NIDCR and regulatory agencies to examine (and when required by applicable law, to copy) research records for the purposes of quality assurance reviews, audits, and evaluation of the study safety, progress and data validity.

Each intervention site (CWRU, UW) will maintain appropriate research records for this study. All records with identifiable information will be kept in secured locked storage units. Only local (e.g., **Outreach Workers**), and CWRU, UW study personnel, the NIDCR Medical Monitor, and NIDCR staff appointed to the trial will have access to the records. Access by the NIDCR Medical Monitor and NIDCR staff is for the purposes of quality assurance reviews, audits, and evaluation of the study safety and progress.

Specific original documents and data records include, but are not limited to:

- Consent chart with all participant-identifying information: Includes signed consent/assent forms, consent documentation, caregiver recruitment and contact form, unanticipated problem or adverse event report forms, and reimbursement logs. These documents will contain the participant's name and other confidential information (e.g. names of child/children and other family members).
- Case Report Forms (CRF): e.g., child baseline and final follow-up ICDAS dental caries assessment form; child baseline and final follow-up dental screening form; Caregiver and IPQ-RD baseline, 2-week follow-up, and final follow-up questionnaires (paper-based and electronic)
- Non-CRF forms: e.g., progress notes checklist (paper-based)
- Recorded audio tapes of Outreach Workers' phone calls (electronic; audio tapes are kept for only 8 weeks)
- Tracking logs
- Memoranda (paper-based)

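### The primary models omit baseline caries severity, which the entry exam already records; adding it could narrow intervals and strengthen the site-specific tests at almost no cost

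*Combined protocol and SAP*

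**What the plan says.** Section 12.2 defines the outcome as "evidence of dental care through restorations or extractions at the final study visit exam that was previously not found during the baseline exam", and adds: "All changes will be recorded on a tooth level using ICDAS criteria".

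Baseline severity is measured with the same instrument. Section 8 introduces the exams as "Dental examinations for baseline caries status and primary study outcome". Section 13 lists among the case report forms the "child baseline and final follow-up ICDAS dental caries assessment form". Section 4.1 admits any child with an "International Caries Detection and Assessment System (ICDAS) active lesion score of 2 or greater", so severity can vary among those who enter. Section 4.2 trims both ends of that range: "Caregivers whose children have no cavities or who have emergent needs will not participate further in the clinical trial".

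The covariates in section 12.4 are socio-demographic only: "Estimated intervention effects (described above) will be adjusted for the following baseline socio-demographic variables: child's age, race, and caregiver SES, education, and marital status". The overall model adds site. Severity is not among the confounders in Table 3.2.1, and it is not a stratification factor (section 5.4.1 uses grade and school). No reason for leaving it out is given.

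**The concern.** The outcome is treatment of diseased teeth. A child with several lesions at entry has more teeth that could show a new restoration or extraction seven months later than a child who barely qualified. Baseline severity is therefore the collected measurement closest to the outcome. It should also be nearly complete, because the exam that yields it decides who is randomized. The planned covariates come largely from a questionnaire whose items caregivers may skip (section 2.3.1).

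When a prognostic baseline variable is left out of a model that already adjusts for others, the standardized relative risk is estimated less precisely and the test loses some power. What is at stake is interval width throughout, and power where it is thin. That means the site-specific tests, which belong to the primary aims in section 12.2 and carry a stated 80%. Section 5.3 reports enrollment below expectation at both sites and a second recruitment year in Ohio districts only, so Washington may have little precision to spare. The documents do not give the number randomized there.

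**Working it through.** **Inputs from section 12.2.** Rates of 19% (standard letter), 37% (CSM letter) and 57% (CSM letter plus DIG); two-sided pooled-variance Z test at 0.05; 102 per arm per site, 204 combined; 5% transfers; stated power 80% per site and 98% combined.

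**Step 1: reproduce the plan's figures.** With d = p2 − p1 and p̄ the mean of the two rates,

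power = Φ{ [d − 1.96·√(2p̄(1−p̄)/n)] / √([p1(1−p1) + p2(1−p2)]/n) }.

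For 19% vs 37% at n = 102: √(0.4032/102) = 0.0629 and √(0.3870/102) = 0.0616, so power = Φ[(0.18 − 0.1232)/0.0616] = Φ(0.922) = 82.2%. For 37% vs 57% it is 82.1%.

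- After 5% transfers, 102 × 0.95 = 96.9. At 97 per arm, power is 80.2% for both contrasts, which matches the stated 80%. That 102 was reached this way is my inference.
- At 204 per arm, power is 98.4% and 98.3%, which matches the stated 98%.
- No covariate enters either figure.

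**Step 2: find where power can be gained.** Section 12.4 tests the standard letter against CSM plus DIG first, and for each contrast tests overall before by site. For 19% vs 57%, power exceeds 99.9% even at 102 per arm. The other two overall contrasts stand at about 98%. That leaves the site-specific tests of 19% vs 37% and 37% vs 57%.

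**Step 3: size the gain.** The documents give no prognostic strength for severity, so the within-arm R² is an assumption. As an approximation, replace n by n/(1 − R²) in the formula above; interval width scales by √(1 − R²). Example: R² = 0.10 gives 102/0.90 = 113.3 and power of 86%. The comparison is severity alone against no covariates.

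| Assumed R² | Per-site power | Combined power | Interval width factor |
|---|---|---|---|
| 0 | 82% | 98.4% | 1.00 |
| 0.02 | 83% | 98.5% | 0.99 |
| 0.05 | 84% | 98.7% | 0.97 |
| 0.10 | 86% | 99.1% | 0.95 |
| 0.20 | 90% | 99.6% | 0.89 |
| 0.30 | 93% | 99.8% | 0.84 |

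The combined gain at the top of the range is 99.8 − 98.4 = 1.4 points.

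**Step 4: check by simulation.** 6,000 trials per setting, 102 per arm, logistic model with a score test, one normally distributed covariate, caregivers treated as independent. The variance ratio is for the standardized log relative risk, adjusted over unadjusted.

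| Within-arm R² (approx.) | 19% vs 37%: variance ratio | Adjusted power | 37% vs 57%: variance ratio | Adjusted power |
|---|---|---|---|---|
| 0 | 1.01 | 83% | 1.01 | 82% |
| 0.04–0.05 | 0.96 | 84% | 0.95 | 85% |
| 0.09–0.12 | 0.91 | 87% | 0.89 | 87% |
| 0.18–0.22 | 0.83 | 90% | 0.80 | 90% |
| 0.26–0.31 | 0.73 | 93% | 0.71 | 94% |

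Unadjusted power in these runs was 82–84%, so the simulation agrees with the approximation. In the R² = 0 row, power went from 83.3% to 83.4% in the first contrast and from 83.4% to 82.0% in the second. The second difference reflects the discreteness of the unadjusted test: its exact power at 102 per arm is 83.8%, against 82.1% from the formula. It is not a cost of the covariate.

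**Step 5: the increment over the planned set.** If the planned covariates explain R²(planned), and the set with severity explains R²(full), the relevant variance ratio is [1 − R²(full)]/[1 − R²(planned)]. Neither quantity is in the documents. The gain over the planned model is smaller than shown to the extent that age, SES or the other covariates already predict severity.

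**The case against.** The strongest reply is that nothing in the plan fails. The covariate set is fixed in advance, randomization protects validity, and the stated power is met without adjustment. The tests that come first have almost no power to gain. The prognostic strength is assumed, and removing children with no cavities or emergent needs narrows the range of severity. The calculation sets severity against no covariates, not against the planned set. The Supplemental Materials list the Statistical Analysis Plan as a separately stored document, which might contain the term.

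Most of this stands, and it limits the size of the claim. It does not remove the case for a change that uses data already collected and costs next to nothing. The text supplied names a concrete covariate set and does not add severity to it.

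Three stronger readings are tempting, and the documents support none of them:

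- **The primary comparison is biased, or left uncorrected for imbalance.** Assignment is randomized, and the test's type I error already allows for chance imbalance in severity.
- **The main overall result loses material power.** It does not (Step 2).
- **The gain can be stated as a number of caregivers saved.** That would need a known prognostic strength and the planned model as comparator. The documents supply neither strength nor increment, and the n/(1 − R²) step is only a device for computing power.

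**Conclusion.** The point holds as a low-cost gain in efficiency. The omission is plain in section 12.4, and severity is the natural covariate for this outcome. Per site, the gain in power runs from about 1 point (R² = 0.02) to 11 points (R² = 0.30), and intervals narrow by about 1% to 16%.

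These figures rest on three assumptions: the R² range, 102 analyzed per arm, and independence between caregivers. They are upper figures for a given R², because the comparator has no covariates.

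The gain in precision refers to the planned estimand, the standardized relative risk. For a conditional log odds ratio, adjustment raises power but need not shrink the standard error.

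**What to change.** In section 12.4, add one prespecified child-level baseline severity term to every primary GEE model: by site, overall, and the version with the site-by-intervention interaction. A suitable term is the number of teeth with an active lesion of ICDAS score 2 or greater at the baseline exam, entered as a single linear term. This uses the entry criterion, so no new cut-off is needed; the supplied text gives no ICDAS threshold for cavitation. A child-level term also fits the model's unit of analysis.

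Standardize the relative risks over this term together with the other covariates, and refit it in each bootstrap sample. Record the choice before outcome data are examined, and check that the separately held Statistical Analysis Plan says the same.

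The cost is one degree of freedom and a sentence or two of text. The data are already on the baseline ICDAS form.

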Dental caries is the leading chronic childhood disease (US DHHS 2000). Its prevalence is steadily increasing, with poor and minority children bearing the brunt. Among 2-11 year-olds, 64% of African American children, 60% of Mexican American children, and 50% of White children had untreated tooth decay (Dye et al. 2007). Nevertheless, despite availability of Medicaid, median dental utilization of low-income children is only 33-37% among the states (Hakim et al. 2012; GAO-08-1121, 2008). This trend highlights why so many children require extensive treatment under general anesthesia (Savage et al. 2004). Untreated primary teeth are a strong predictor of future caries indicating the chronicity of the disease (Birkeland et al. 1976; Bader et al. 1986; Van Palenstein et al. 2001; Motohashi et al. 2006). Untreated decay can lead to serious infections and pain, interference with eating/speaking, overuse of EDs, and lost school time (Edmunds et al. 1998). Early preventive care has been shown to reduce later downstream costs (Savage et al. 2004). Poorer oral health-related quality of life was found among preschoolers with ECC (Leal et al. 2012; Martins-Junior et al. 2012; Kramer et al. 2013) and among school children from low-income households (Locker 2007).

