Confounders	Child's age, race, dental visit Caregiver socio-demographics (age, race, SES, education, marital status)	Baseline	NHANES IV
Subject compliance with Intervention	
 • Whether the referral letter (and DIG) was received (generic code) • Whether the referral letter (and DIG) was read/understood (Postcard) 	Within 2 days after Baseline dental exam	

1. **Baseline:** prior to screening dental exam; **At randomization:** after baseline dental screening exam; **Two-weeks:** Two weeks after randomization; **Exit:** two weeks before end of school year dental exam

2. Caregiver self-efficacy and subjective norms will also be considered as potential **mediators** in the additional mediational analyses, and will be measured at the **Exit** in addition to **Baseline**.

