12.4 Final Analysis Plan

Primary Statistical Analysis: Descriptive statistics will include frequencies (categorical variables) and means (continuous variables) of baseline covariates among the five intervention groups. Chi-square tests (for categorical variables) and t-tests (for continuous variables) will be performed to test for group differences (by site and overall). In our primary analysis, we will fit multivariate generalized linear (specifically, logistic regression) models with dental care receipt as the (binary) outcome and the child as the unit of analysis (as receipt of dental care will be determined for each child). A generalized estimating equations (GEE) approach (with an exchangeable working correlation structure) will be used to allow for correlations among multiple children for a given caregiver. Separate models will be fit for each site as well as overall. The models will include two indicator variables representing the three interventions. Each model will include an a priori selected set of

baseline variables (listed below) and, for the overall model, an indicator variable for site. Secondarily, we will fit a model with a site by intervention group interaction, and the latter will be tested to formally assess possible intervention effect heterogeneity over sites.

We will also consider working correlation structures (e.g., alternating logistic regressions) that allow for second-level clusters, namely schools (within which the first-level cluster, caregiver, is nested). We will determine final models based on the quasi-likelihood information criterion (QIC). Intervention (and other covariate) effects will be tested using generalized score statistics.

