- d) Clinic
- e) Other, please specify _____

8.8. Sometimes people have trouble getting all the dental treatment they need. During the *past 12 months*, was there any time when your child needed dental care but it was delayed or not received?

- a) Yes → Please answer Questions 8.8a and 8.8b
- b) No
- c) Don't know

Please skip to Question 8.9

8.8a. What type of treatment was delayed or not received after a problem had been found by a dental provider? Please circle all that apply.

- a) Filling
- b) Extraction [having a tooth pulled]
- c) Crown / metal cap
- d) Pulp therapy [baby root canal]
- e) Gum disease
- f) Other, please specify _____
- g) Don't remember

Study Site _____ ID# _____

Caregiver Questionnaire-Baseline

8.8b. Why did your child NOT get all the dental care that he/she needed? Here are some common reasons from other parents — please circle all that apply.

- a) The cost is too much.
- b) My child does not have dental insurance or Medicaid.
- c) My family has a problem with our health care plan.
- d) I cannot find a dentist who accepts my child's insurance.
- e) There are no available dentists in my area. / I have transportation problems.
- f) It is difficult to get convenient appointment times. / My child could not get an appointment.
- g) The dentist did not know how to treat or provide care for my child.
- h) I was dissatisfied with the dentist.
- i) I did not know where to take my child for treatment.
- j) My child refused to go.
- k) My child's treatment is ongoing.
- l) My child needed a referral and we could not get one.
- m) Other, please specify _____

8.9. During the past 12 months, did you, a doctor, or a dentist think your child needed to see a dental specialist (for example, a pediatric dentist)?

- a) Yes → Please answer Question 8.9a
- b) No
- c) Don't know

8.9a. During the past 12 months, how much of a problem—if any—was it to get the care from the specialist that your child needed?

- a) Big problem
- b) Small problem
- c) Not a problem
- d) Don't know

8.10. A personal dentist is a health professional who knows your child well and is familiar with your child's dental health history. Do you have one or more persons that you think of as your child's personal dentist?

- a) Yes, 1 person
- b) Yes, more than 1 person
- c) No

THANK YOU!

16

Site: _____ ID# _____

Family Access to Dentist Study

**Your Feelings
About Cavities**

January 29, 2015

2-week Follow-up

Site: _____ ID# _____

Instructions:

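### Section 12.4 omits the child's prior dental visit from the prespecified covariates although Table 3.2.1 names it as a confounder; the cost is precision, not bias

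*Combined protocol and SAP*

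**What the plan says.** Table 3.2.1 (under section 3.2.2) has a row of confounders measured at baseline. The child-level entry is "Child's age, race, dental visit". The caregiver-level entry is "Caregiver socio-demographics (age, race, SES, education, marital status".

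Section 12.4 describes logistic models for receipt of care, fitted by GEE with the child as the unit, per site and overall. It says "Each model will include an a priori selected set of" baseline variables, to be listed further down, plus a site indicator in the overall model. The list, under the adjustment paragraph of 12.4, is the child's age, "race, and caregiver SES, education, and marital status". No other text in 12.4 adds to it.

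The information is collected before randomization. In the Baseline Caregiver Questionnaire (Appendix C), item 8.2 asks whether the child has ever seen a dentist. Item 8.4 asks for the number of preventive dental visits in the past 12 months, leaving out visits made because of pain or a problem.

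**The concern.** Of the confounders in Table 3.2.1, whether the child has recently been to a dentist is the one closest to the outcome, and it is the child-level entry that 12.4 drops. Randomization is stratified by grade and school only (section 5.4.1), so prior attendance is balanced only on average.

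Site-specific comparisons are part of the primary aim (section 12.2) and are planned at only 80% power, so a prognostic covariate is worth most there. Section 5.3 reports lower than expected enrollment at both sites and places the extra recruitment year in Ohio districts only, so Washington has little slack. The data already exist. The remaining question is whether the variable is named before the results are known; a covariate added afterwards would look chosen.

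**Working it through.** **1. The two lists side by side.**

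| Table 3.2.1, confounders | In the 12.4 set? |
|---|---|
| Child's age | Yes |
| Child's race | Yes |
| Child's dental visit | No |
| Caregiver age | No |
| Caregiver race | Unclear; the wording reads as the child's race |
| Caregiver SES, education, marital status | Yes |

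**2. The plan's own power.** Inputs from section 12.2: 19% versus 37%, pooled two-sided Z test, alpha 0.05, 102 per arm per site.

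z = [0.18 × √102 − 1.96 × √(2 × 0.28 × 0.72)] / √(0.19 × 0.81 + 0.37 × 0.63) = (1.818 − 1.245) / 0.622 = 0.92, so power is 82.2%.

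For 80%, 97 per arm suffice, and 97/0.95 = 102.1. The stated 80% with 102 is therefore consistent with a 5% allowance for transfers. At 204 per arm, power is 98.4% (stated: 98%).

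**3. Bias and type I error.** Simulation: 102 per arm, half the children with a prior visit, overall control rate 19%, 3,000 runs per setting, no treatment effect. With control rates of 14% versus 24%, 9% versus 29% and 4% versus 34% (no prior visit versus prior visit), the unadjusted test rejects in 5.7%, 5.1% and 4.7% of runs. The mean difference between arms is within 0.1 point of zero in all three.

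**4. Power with and without the covariate.** The same settings, with a within-stratum log-odds effect of 1.0 or 0.92. The latter is the planned effect: ln[(0.37/0.63)/(0.19/0.81)] = 0.92.

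| Control rates (no visit / visit) | Log-odds effect | Unadjusted | Adjusted | Gain (points) |
|---|---|---|---|---|
| 14% / 24% | 1.0 | 86.9% | 87.4% | 0.5 |
| 9% / 29% | 1.0 | 82.0% | 84.9% | 2.9 |
| 4% / 34% | 1.0 | 69.1% | 77.4% | 8.3 |
| 14% / 24% | 0.92 | 80.2% | 80.6% | 0.4 |
| 9% / 29% | 0.92 | 74.6% | 78.4% | 3.8 |
| 4% / 34% | 0.92 | 62.4% | 71.9% | 9.5 |

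Read across rows only: the same log-odds effect gives a smaller overall difference as the gap widens (19.3, 17.9 and 15.1 points at 1.0). Each power figure has a simulation standard error of about 0.6 to 0.9 points, for example √(0.87 × 0.13/3000) = 0.6 points.

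**5. Rough cross-check.** With half the children having a prior visit and a gap g, the share of outcome variance explained is 0.25 g²/(0.28 × 0.72): 1.2%, 5.0% and 11.2% for g = 0.10, 0.20 and 0.30. Taking the effective n as 102/(1 − R²), power goes from 82.2% to 84.1% at R² = 5% and to 86.0% at 10%. These gains are somewhat smaller than the simulated ones but of the same order.

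**6. Combined sample.** R² between 2% and 20% moves power only from 98.4% to between 98.5% and 99.6%.

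**The case against.** The omission may be deliberate. Section 12.4 calls its list socio-demographic, and a prior dental visit is not that. Caregiver age is missing too, which suggests a chosen subset rather than one slip. Table 3.2.1 classifies variables for the whole conceptual model, where confounding matters for the mediation paths; randomization takes care of the arm comparison. The supplemental materials also name a separately stored Statistical Analysis Plan, which may hold a fuller list. All this is possible, but 12.4 gives no reason and its mediation text names no covariates either. As written, a variable labelled a confounder is assigned to no analysis. If the separate plan includes it, 12.4 still needs to match.

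The cost of chance imbalance should not be counted twice. A one-SD imbalance in prior visits at 102 per arm is √(0.25 × 2/102) = 7 points, which moves a site-level difference by 1.4 to 2.1 points for a 20- to 30-point gap. The standard error of that difference, √(0.28 × 0.72 × 2/102) = 6.3 points, already contains this. That stands: the loss is in precision, not in validity.

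It also stands that the gains rest on assumed inputs, that they are measured against no adjustment at all (the covariates already planned may capture part of them), and that item 8.4 records preventive visits only.

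**Conclusion.** The two lists disagree, and 12.4 should be corrected or the difference explained. The consequence is lost precision, mainly per site: about 0.5, 3 or 8 points of power for a 10-, 20- or 30-point gap, assuming half the children had a prior visit and a log-odds effect of 1.0. The documents give neither the share nor the gap. The overall comparison, tested first, has about 98% power and hardly changes.

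Three stronger readings are not supported.

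- A reader might infer that a missing confounder biases the primary result. Assignment is random, and the simulation shows neither bias nor an excess of false positives.
- A reader might infer that care already under way makes up much of the outcome, by taking "median dental utilization of low-income children is only 33-37% among the states" as annual and scaling by 7/12 to 19–22%, close to the planned 19% control rate. That figure is general utilization. The outcome requires a new restoration or extraction in a child selected for an active lesion, and the 19% comes from referred children who later received care, so it already contains background care. Nor would adjustment undo any dilution from such care.
- A reader might infer that the baseline form identifies children in treatment through option k of item 8.8b ("treatment is ongoing"), so that they could be excluded in a sensitivity analysis. That item is reached only after a Yes to care having been delayed or not received, so children whose treatment is proceeding normally never see it.

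**What to change.** Before unblinding, amend the adjustment paragraph of 12.4:

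- Add the child's prior dental visit, defined as baseline item 8.4, any versus none in the past 12 months, and state that the item counts preventive visits only.
- Add caregiver age or say why it is left out, and make clear whose race is meant, so that 12.4 and Table 3.2.1 agree.
- Give a rule for missing baseline answers, such as a missing category. The missing-data text in 12.4 covers the questionnaire outcomes, not covariates of the primary model. For caregivers with several children, say which child's answer applies.

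If the omission is intended, one sentence giving the reason would do instead. The cost is a few lines of text and one or two more model terms, with no new data collection. No sensitivity analysis based on item 8.8b is needed.
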